9.3 Study Duration

Subjects will attend study visits from the time of signed informed consent through 12 months (efficacy portion) and a 5 year follow-up period after the first Therapeutic Dose of Ultratrace iobenguane I 131. Subjects will be monitored for AE/SAE and Adverse Events of Special Interest (including post radiation toxicity) as described in Section 12. Subjects may undergo additional assessments to confirm response, or as part of institutional standard of care during long-term follow-up. Figure 1 outlines the study period; a more extensive summary of study procedures is given in the Schedule of Procedures (Appendix VII).

FIGURE 1: STUDY DURATION

Signed informed consent, subject enters study Eligibility/dosimetry study Imaging Dose (3 to 6 mCi) of Ultratrace iobenguane I 131 administered within 30 days of first therapeutic dose followed by three I 131 whole body scans to confirm uptake and to determine dosimetry First Therapeutic Dose of Ultratrace iobenguane I 131 administered day 0 I 131 scan within seven days post first therapeutic infusion to assess biodistribution Safety visit 6 weeks post-first Therapeutic Dose Objective tumor response assessments 3 months post-Therapeutic Dose and prior to the second Therapeutic Dose Second Therapeutic Dose Ultratrace iobenguane I 131 administered starting at month 3, at least 12 weeks after the first Therapeutic Dose. I 131 scan within seven days after second Therapeutic Dose Safety visit 6 weeks post second Therapeutic Dose Tumor response assessments, tumor markers (every two weeks through week 24 and monthly from month 7-12), physical exam at months 3 (prior to the second Therapeutic Dose, if administered), 6, 9 and 12 Subject completes regularly scheduled study visits at month 12 Long-term follow-up for adverse events of special interest, overall survival, tumor markers and disease status (inc. clinical benefit) through year 5

9.4 Study Population

It is anticipated that the study will enroll approximately seventy-five subjects to ensure a total of 58 subjects given two doses of Ultratrace iobenguane I 131 will be evaluable for efficacy and safety. All subjects who received at least one Therapeutic Dose of Ultratrace iobenguane I 131 will be included in the Full Analysis Set; all subjects who received both Therapeutic Doses and who attended the 3 Month and 6 Month Efficacy Visits with no major protocol violations will be included in the Per Protocol Set. The primary endpoint, proportion of subjects experiencing a reduction in use of antihypertensive medication for at least six months or two cycles, will be analyzed separately for each of these populations.

Safety analyses will include treatment emergent adverse events, clinical laboratory measurements, vital signs measurements, and physical examination findings. All subjects who received the Imaging Dose of Ultratrace iobenguane I 131 will be included in the analysis of any

safety endpoint. Adverse events will be captured for all enrolled subjects and those prior to the Imaging Dose will be displayed in a separate listing.

9.5 Inclusion Criteria

To participate in this study, subjects must meet all of the inclusion criteria listed below.

All subjects must:

- 1. Provide written informed consent (and assent for subjects less than 18 years of age) and be willing to comply with protocol requirements
- 2. Be at least 12 years of age
- 3. Have a documented (medical record) diagnosis of either pheochromocytoma or paraganglioma that was confirmed by histology or a physician using other supportive data (e.g. abnormal MIBG diagnostic study, or elevated tumor markers).
- 4. Be ineligible for curative surgery for pheochromocytoma
- 5. Have failed a prior therapy for pheochromocytoma/paraganglioma or are not candidates for chemotherapy or other curative therapies
- 6. Be on stable antihypertensive medication regimen for tumor-related hypertension for at least 30 days prior to the first therapeutic dose. A stable antihypertensive medication regimen is defined as no addition or deletion of antihypertensive medication and no change in total daily dose or route of administration for currently used antihypertensive medication(s) in the 30 days prior to first therapeutic dose.
- 7. Have at least one tumor site by CT or MR or iobenguane I 131 scan
- 8. Have definitive MIBG tumor avidity
- 9. Have an expected survival period of at least 6 months as prognosticated by physician

Female subjects must:

- 10. Have a negative pregnancy test within 48 hours prior to receiving Ultratrace iobenguane I 131
- 11. Agree to use an acceptable form of birth control (abstinence, IUD, oral contraception, barrier and spermicide or hormonal implant) during this study and for 6 months following Therapeutic Doses of Ultratrace iobenguane I 131. For those women who are sexually active and using oral contraceptives, a second form of barrier contraception is required. or
- 12. Not be of childbearing potential as documented by history (e.g., tubal ligation or hysterectomy) or is post menopausal with a minimum of 1 year without menses

Male subjects must:

- Agree not to father a child during the period beginning immediately after administration of the first Therapeutic Dose of Ultratrace iobenguane I 131 during the study and ending six months after administration of the last Therapeutic Dose of Ultratrace iobenguane I 131.
- 14. Use an acceptable method of birth control (e.g., vasectomy or as described above) during the study and for six months following the Therapeutic Doses of Ultratrace iobenguane I 131.

9.6 Exclusion Criteria

Subjects will be excluded if any of the following conditions are observed:

- 1. <50% of FDG (if data are available) positive lesions are MIBG avid
- 2. Pregnant or nursing females
- 3. Active CNS lesions by CT or MR scanning within 3 months of study entry
- 4. New York Heart Association class IV heart failure, symptomatic congestive heart failure [New York Heart Association class IV with another medical disorder], unstable angina pectoris, cardiac arrhythmia
- 5. Received any previous systemic radiotherapy resulting in marrow toxicity within 3 months of study entry or have active malignancy (other than pheochromocytoma/paraganglioma) requiring additional treatment during the active phase or follow up period of the Ultratrace iobenguane I 131 trial. (Prior iobenguane I 131 therapy is allowed if not within 3 months prior to the first therapeutic dose).
- 6. Administered prior whole-body radiation therapy
- 7. Received external beam radiotherapy to > 25% of bone marrow
- 8. Administered prior chemotherapy within 30 days of study entry or have active malignancy (other than pheochromocytoma/paraganglioma) requiring additional treatment.
- 9. Karnofsky Performance Status is < 60
- 10. Platelets $\leq 80,000/\mu L$
- 11. Absolute neutrophil count (ANC) \leq 1,200/µL
- 12. Total bilirubin > 1.5 times the upper limit of normal
- 13. AST/SGOT or ALT/SGPT ≥ 2.5 times the upper limit of normal
- 14. Diagnosed with AIDS or HIV-positive per patient medical history
- 15. Active chronic alcohol abuse, chronic liver disease (excluding liver metastases), or hepatitis (A, B or C, detected by positive testing for HbsAg and anti-HCV as stated in patient medical history)
- 16. Renal dysfunction/impairment (defined as creatinine clearance of <30 mL/min or Glomerular Filtration Rate (GFR) of <30mL/min) because of the possibility of delayed Ultratrace iobenguane I 131 excretion and increased whole body dose
- 17. Known allergy to iobenguane that has required medical intervention
- 18. Received a therapeutic investigational compound and/or medical device within 30 days before admission into this study
- 19. Receiving a medication which inhibits tumor uptake of iobenguane I 131 as described in Appendix III of the protocol
- 20. Any medical condition or other circumstances (i.e., uncontrolled current illness including but not limited to, ongoing or active infection or psychiatric illness/social situations that would limit compliance with the study requirements.)
- 21. Any other condition, that in the opinion of the investigator, may compromise the safety or compliance of the subject or would preclude the subject from successful completion of the study

9.7 Discontinuation Criteria

The reason for the subject's discontinuation will be clearly documented on the case report form (CRF). Discontinued subjects may be replaced with written authorization from MIP. Subjects will be discontinued from the study if the subject:

- withdraws consent
- experiences progressive disease
- receives another anticancer therapy
- is lost to follow up
- experiences an adverse event leading to discontinuation

If a subject discontinues the study within 6 weeks following a Therapeutic Dose infusion of Ultratrace iobenguane I 131, the Investigator will contact the subject via telephone or other appropriate means to follow up 6 weeks post-infusion.

9.8 Visits for Discontinued Subjects Not Withdrawing Consent

Unless consent has been withdrawn, discontinued subjects should continue to receive all scheduled assessments other than CT/MR/bone scans and tumor marker lab tests, and the subjects should also be entered on long-term follow-up to be followed for overall survival and late radiation toxicity.

Subjects who meet discontinuation criteria, but do not withdraw consent can continue to be followed as described below:

Subjects discontinuing within 6 weeks of either therapeutic iobenguane I 131 infusion are to be assessed at the Safety Visit. After this safety checkpoint, subjects can continue to be followed on the Efficacy Visit schedule until Month 12 receiving all scheduled assessments other than CT/MR/bone scans and tumor marker lab tests. After the Month 12 Efficacy Visit, the subject may enter the Long-Term Follow-Up (LTFU) to be followed another 4 years for a total of 5 years from the first therapeutic dose.

Subjects discontinuing during the Efficacy Visit Phase can continue to be followed on the Efficacy Visit schedule until Month 12 receiving all scheduled assessments other than CT/MR/bone scans and tumor marker lab tests. After the Month 12 visit, the subject may enter the LTFU period to be followed another 4 years for a total of 5 years from the first therapeutic dose.

For subjects wanting to withdraw consent during the efficacy portion of the study (the first 12 months), every effort shall be made to have these subjects return for a final visit and perform the procedures delineated for the Month 12 visit.

Subjects discontinuing during the Long-Term Follow-up period will only be followed for adverse event of special interest. The follow-up discussion may occur via telephone, for subjects who are being followed only for adverse events of special interest.

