Safety will be assessed through analyses of treatment emergent adverse events (AEs), as well as baseline and pre- and post-infusion ECGs, physical examinations, vital signs measurements, laboratory measurements (including clinical chemistry, hematology and urinalysis), and human radiation absorbed dose estimates to target lesions and normal organs. Subjects will be monitored for serious and non-serious AEs, and Adverse Events of Special Interest see Section 12.

After the 12 month assessment, subjects enter long-term follow-up and remain in follow-up for 5 years following the first therapeutic dose. Subjects will be followed for overall survival for 5 years following the first therapeutic dose. In years 2-5 post-treatment (or until a patient experiences disease progression, start of another anticancer therapy or death), data on tumor response, tumor markers and clinical benefit (including use of antihypertensive medication) will be collected through assessments provided as institutional standard of care. If standard of care is not providing such assessments, they will be offered by the study site.

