12.1.2 Reporting Serious Adverse Events

Serious is a regulatory definition and is based on subject or event outcome or action criteria usually associated with events that pose a threat to a subject's life or functioning. Seriousness (not severity) serves as the guide for defining the sponsor's regulatory reporting obligations (i.e., to the applicable regulatory authorities). Adverse event severity and seriousness should be assessed independently by investigators.

MIP, as Sponsor of the study, is responsible for reporting relevant SAEs as safety reports to the FDA, Health Canada and other applicable regulatory authorities, and participating Investigators, in accordance with the US Code of Federal Regulations (CFR) Title 21 CFR 312.32 and 312.33, European Clinical Trials Directive, ICH guidelines, Health Canada guidelines, Good Clinical Practice and/or local regulatory requirements.

The Investigator must report all SAEs to MIP designee within 24 hours, by telephone, email or fax, and confirm that the information was received (see Appendix VIII).

A Serious Adverse Event Report (SAER) must be completed by the Investigator or designee and faxed or emailed to MIP's designee within 24 hours after the Investigator first becomes aware of the serious event. A separate SAER will be needed for each reported SAE so that the onset, resolution date causality and outcome can be assessed for each event. Any source documents relevant to the event should be forwarded to MIP's designee with the SAER form. The SAER form must be signed and dated by the Investigator. The Original copy must remain on site with the CRF.

In case of death, a comprehensive narrative report of the case should be prepared by the Investigator and sent to MIP's designee, together with the SAER. If an autopsy is performed, a copy of the autopsy report should be actively sought by the Investigator and sent to the Sponsor or designee as soon as available. A copy of the autopsy report must remain on site with the CRF.

All deaths will be reported as SAEs regardless of their relationship to disease progression and reported via an SAER form from the time of signed informed consent until completion of the follow up period. All other SAEs will be reported until the last day of Week 15 following the last administration of Ultratrace iobenguane I 131, and reported via an SAER form to MIP's designee.

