7.4.11. Overall Survival

Overall survival (OS) is defined as the time from the date of first therapeutic dose to the date of death from any cause. OS time will be censored at the last date the subject is known to be alive. The Kaplan-Meier predicted survival rates at Years 1-5 will be reported. Overall survival will be listed and Kaplan-Meier curves will be prepared. The last date that the patient was confirmed to be alive will be obtained from information reported by the clinical site: if this information is collected outside of the CRF the last date the subject is known to be alive or date of death reported from the site will be provided in a spreadsheet and integrated into analysis datasets.

Overall survival will also be presented by primary endpoint status.

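### Protocol 9.8 contradicts itself and the 5-year survival follow-up: subjects who discontinue during long-term follow-up are limited to AESI follow-up, which risks informative censoring of overall survival

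*Protocol*

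**What the plan says.** **Who discontinues.** Protocol 9.7 lists the reasons for discontinuation. They include a subject who "experiences progressive disease" or who receives another anticancer therapy. Neither is confined to the first 12 months.

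**What follows.** Protocol 9.8 gives two answers for subjects who have not withdrawn consent.
- First paragraph, for discontinued subjects in general: "the subjects should also be entered on long-term follow-up to be followed for overall survival and late radiation toxicity".
- Last paragraph, for those already in long-term follow-up: "Subjects discontinuing during the Long-Term Follow-up period will only be followed for adverse event of special interest". It adds: "The follow-up discussion may occur via telephone, for subjects who are being followed only for adverse events of special interest".

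**The survival commitment.** Protocol 9.1 states: "Subjects will be followed for overall survival for 5 years following the first therapeutic dose". The Study Outline, Protocol 11.5.17 and SAP 4.1 say the same in substance, and survival up to 5 years is a secondary objective.

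**Deaths and censoring.** Protocol 12.1.2 states: "All deaths will be reported as SAEs regardless of their relationship to disease progression", from consent until the follow-up period is complete. For survival, SAP 7.4.11 states: "OS time will be censored at the last date the subject is known to be alive"; Protocol 13.3.2.2.8 has the same rule. The SAP takes the date from the site, including from outside the CRF. It reports Kaplan-Meier rates at Years 1-5 and presents survival by primary-endpoint status.

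**The concern.** Taken together, 9.7 and the last paragraph of 9.8 treat two progressors differently. One who progresses in Year 1 is kept in follow-up for survival to Year 5. One who progresses in Year 2 or later is, on the literal text, followed for AESIs only. If the site then stops recording vital status, the last date known alive stays close to the date of progression.

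Progression usually raises the risk of death, so losing vital status at that point is informative. Kaplan-Meier assumes that censored subjects have the same future risk as those still observed. If the censored subjects are at higher risk, the curve at Years 2-5 is too high. The comparison of survival by primary-endpoint status could also be distorted if late progression is more common in one group. Deaths after late progression are safety information too.

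**Working it through.** **1. Which provisions apply to a Year 2-5 progressor who has not withdrawn consent?**

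| Provision | Survival follow-up after late progression? |
|---|---|
| Protocol 9.8, first paragraph | Yes |
| Protocol 9.8, last paragraph | No; AESIs only |
| Protocol 9.1, Study Outline, Protocol 11.5.17, SAP 4.1 | Yes; no stop at progression stated for survival |
| Protocol 12.1.2 | Deaths yes, until the follow-up period is complete; no last-alive date |
| SAP 7.4.11, Protocol 13.3.2.2.8 | Censor at last date known alive |

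The first paragraph of 9.8 does not clearly override the last. It speaks of entering subjects on long-term follow-up, which fits those not yet in it. The last paragraph is the specific rule for those already there.

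**2. Is there a figure in the plan to reproduce?** No. The documents state no expected survival rate, event count or sample size for survival. What follows is an illustration on assumptions.

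**3. Model.** Three states (progression-free, progressed, dead) with constant hazards:
- λ, progression. Protocol 7.2 cites a carrier-added series in which 35% progressed within a year. Taking 65% progression-free at 1 year, λ = −ln 0.65 = 0.431 per year.
- μ0, death without progression: assumed 0 or 0.03 per year.
- μ1, death after progression: solved so that true 5-year survival is 40% or 64%. Both figures appear in the Protocol as background (40% in 7.1; 64% in 7.2 for the same series as the 35%).

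Subjects who progress before month 12 keep survival follow-up. Those who progress later are (A) all censored at progression, (B) half censored at progression, or (C) fully followed. About half of all subjects (0.49 to 0.53) progress between Years 1 and 5. Each scenario used 400,000 simulated subjects.

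| True 5-year OS | μ0 | μ1 | A: none captured | B: half captured | C: all captured |
|---|---|---|---|---|---|
| 0.400 | 0 | 0.379 | 0.568 (+16.8 points) | 0.455 (+5.5) | 0.400 (0) |
| 0.400 | 0.03 | 0.334 | 0.518 (+11.8) | 0.440 (+4.0) | 0.400 (0) |
| 0.640 | 0 | 0.164 | 0.718 (+7.8) | 0.668 (+2.8) | 0.640 (0) |
| 0.640 | 0.03 | 0.136 | 0.685 (+4.5) | 0.656 (+1.6) | 0.640 (0) |

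Rounded, A gives +5 to +17 points and B gives +2 to +6.

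**4. Check of the first row without simulation** (μ0 = 0).
- Early progressors alive at 1 year: E(1) = λ/(λ−μ1) × (e^(−μ1) − e^(−λ)) = 0.287. Survival at 1 year = 0.650 + 0.287 = 0.937.
- Under A, the only deaths seen after Year 1 are among early progressors. Their share of the risk set is 0.307 at Year 1, 0.329 at Year 3 and 0.352 at Year 5.
- The cumulative observed hazard over Years 1-5 is about 4 × 0.379 × 0.329 = 0.499.
- Kaplan-Meier at 5 years = 0.937 × e^(−0.499) = 0.569. This agrees with 0.568.

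**5. Sensitivity.** With 50% to 80% progression-free at 1 year, A ranges from about +2 to +38 points and B from about +1 to +14. C is 0 throughout. The size depends heavily on unknown hazards and on how much is captured; the direction does not change over this grid.

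**The case against.** The strongest reply is that one loose sentence stands against the rest of the plan. Protocol 9.1 says what ends at progression: "In years 2-5 post-treatment (or until a patient experiences disease progression, start of another anticancer therapy or death), data on tumor response, tumor markers". Collection of clinical-benefit data stops there too. Survival is not in that list. All deaths are reportable whatever their relation to progression. AESI contacts continue, and a site that makes such a contact learns whether the subject is alive. The SAP accepts last-alive dates from outside the CRF.

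Most of this stands. A reader might infer that the plan censors survival at progression and that the 5-year estimate is therefore biased upward. The documents do not support that: no section sets such a censoring rule, and capture as the other sections intend gives no bias from this source.

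The reply does not remove the problem, for three reasons.
- Protocol 12.1.2 does not say when the follow-up period is complete for someone discontinued from long-term follow-up. If it ends at discontinuation, the same section then asks only for deaths believed related to the product, and deaths from progression would fall outside it.
- Death reports alone do not supply the last-alive dates of survivors.
- Nothing in 9.8 asks for a last-alive date at the AESI contact.

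It is also fair to say that the size in scenario A is a worst case. The death hazards are assumed, and the progression rate comes from a different preparation of the drug.

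**Conclusion.** The contradiction is established from the text: the last paragraph of 9.8 cannot be reconciled with 5-year survival follow-up once 9.7 makes late progression and new therapy grounds for discontinuation. Upward bias is a conditional risk. It arises only if sites apply the last paragraph literally and vital status is lost after late progression.

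On the stated assumptions, the 5-year rate would then be overstated by about 5 to 17 points with no capture, or 2 to 6 with half. These are illustrations, not predictions for this trial. Overall survival is a descriptive secondary endpoint with no success criterion, so the primary endpoint, its significance level and the sample size are untouched. The wording should be corrected, but it does not threaten the trial's main conclusion.

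**What to change.** 1. Reword the last paragraph of Protocol 9.8. Subjects who discontinue during long-term follow-up, unless they withdraw consent, are followed for AESIs and vital status (date last known alive, date and cause of death) at the existing six-monthly contact until 5 years after the first therapeutic dose. Telephone contact can remain.
2. State in Protocol 12.1.2 that completion of the follow-up period means that 5-year point, not the date of discontinuation.

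The cost is a short amendment and one extra question at a contact already in the schedule (Appendix VII). Protocol 7.6 shows that the sponsor already collects these vital-status items in study MIP-IB13. Where dates have already been missed, SAP 7.4.11 allows site-reported dates from outside the CRF to be added to the analysis datasets, so no SAP change is needed.
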